
Figure 4. Overview of the study time points.

deviate from the standard of care typically provided to patients undergoing ACL-R. An overview of the timeline of study visits is presented in Figure 4 and Table 1. This study is registered on Clinicaltrials.gov (NCT02420353) and was granted an IND exemption by the FDA (IND 123189).

| Study Visit | Measures Performed |
|-------------------------------------|---|
| 1. Preop 1 (~4 wk prior to surgery) | History/vitals, blood draw, vital signs |
| 2. Preop 2 (~2 wk prior to surgery) | Surveys, BioDex (isometric, isokinetic), MRI, medication instruction, vital signs |
| 3. Postop 1 (~1 wk after surgery) | Surveys, blood draw, medication check, vital signs |
| 4. Postop 2 (~2 wk after surgery) | Surveys, blood draw, medication check, vital signs |
| 5. Postop 3 (~5 wk after surgery) | Surveys, BioDex (isometric, isokinetic), MRI, blood draw, medication check, vital signs |
| 6. Postop 4 (~12 wk after surgery) | Surveys, BioDex (isometric, isokinetic, balance), blood draw, vital signs |
| 7. Postop 5 (~18 wk after surgery) | Surveys, BioDex (isometric, isokinetic, balance), blood draw, vital signs |
| 8. Postop 6 (~26 wk after surgery) | Surveys, BioDex (isometric, isokinetic, balance), MRI, blood draw, vital signs, patient discharged from the study |

Table 1. Timeline of study visits and measures performed in this proposal.

Patient Selection and Recruitment. This study is based on an already approved protocol by the University of Michigan Medical School Institutional Review Board (study # HUM00038126). All patients will provide informed consent prior to participating in the study.

Inclusion Criteria:

1. Males between the ages of 18 and 35
2. Have acute unilateral complete ACL tears with or without bucket handle medial meniscus tears that occurred within the past 6 months
3. Consent to undergo an ACL reconstruction by [name] using a patellar tendon or hamstring autograft
4. Will be performing supervised post-operative rehabilitation at UMHS MedSport at Dominos Farms ([name])

Exclusion Criteria:

1. Patients who are undergoing a revision ACL reconstruction
2. Had a previous injury to the involved knee
3. Have an allergy to recombinant GH
4. Have a BMI < 20 or > 35

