Surveys and Recording of Patient-Reported Adverse Events. Patients will complete patient reported outcome measure (PROM) surveys at each visit to measure pain, function and physical performance, including (i) the Veterans Rand-12 (VR-12), to measure overall health-related quality of life (Selim 2009); (ii) the International Knee Documentation Committee (IKDC) survey, to evaluate knee-specific sports function (Anderson 2006), and (iii) the Knee injury and Osteoarthritis Outcome Score (KOOS), to evaluate knee-specific general and sports function (Roos 2003). Patients will also be asked to report adverse events associated with the use of GH, as described in the GH Self Reporting Symptom Form.

BioDex Strength Testing and Ultrasound Muscle Cross-Sectional Area Measurements. Whole muscle isometric and isokinetic strength measurements will be performed in a BioDex System 3 dynamometer as described (Mendias 2013). Maximum isometric force will be measured at 45° and 90° of knee flexion. Maximum isokinetic flexion and extension will be measured over a 90° arc at a velocity of 60°/second. All measures will be performed bilaterally, and the highest force from a series of five trials from each side will be used.

MRI Muscle Volume Measurements. Bilateral MRI scans will be performed at the pre-operative, third post-op and sixth post-op visit. Scans will be performed in a 3.0T magnet and will extend from hip to knee. The volume of the quadriceps and hamstring muscle groups will be determined using quantitative MRI analysis software.

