Blood Draw. Approximately 6-8mL of blood will be drawn from an antecubital vein and collected into either a K₂-EDTA tube for plasma preparation or a clot activator tube for serum preparation. A portion of the plasma or serum will be used for clinical labs performed by UMHS M-Labs and a portion will be stored at -80°C for measurement of different proteins in [name] lab. The tests performed by M-Labs include a complete blood count with platelet differential, metabolic panel (glucose, urea nitrogen, creatinine, sodium, potassium, chloride, CO₂, calcium, total protein, albumin, total bilirubin, AST, ALT and alkaline phosphatase), lipid panel (total cholesterol, triglycerides, HDL cholesterol, LDL cholesterol), hemoglobin A_{1c}, high sensitivity CRP, creatine kinase, and IGF-1. For measurements performed in [name] lab, the levels of myostatin (as a marker of muscle atrophy), MMP-3 (as a marker of cartilage catabolism), and hyaluronic acid (as a marker of cartilage catabolism) will be measured in duplicate using ELISAs as described (Mendias 2013).

Vital Signs. Patients' heart rate, temperature, blood pressure and respiratory rate will be recorded at each visit.

Wallet Card. Patients will be provided with a laminated card to carry in their wallet or purse in case of emergencies. The card will state that the patient is currently enrolled in a clinical trial evaluating GH, that they are taking either GH or placebo and the contact information for [name], [name], [name] and the study research coordinator.

Administration of GH or Placebo. The UMHS Pharmacy IDS service will be used to assist with storing, preparing and dispensing drug. We will use Humatrope (somatropin of rDNA origin, Eli Lilly) as the test drug, and sterile bacteriostatic saline with no active hormone will serve as the control. We will use sterile insulin syringes to deliver drug or placebo subcutaneously. Patients will be provided with the manufacturer's instructions for the use of Humatrope, all supplies (needles, alcohol swabs, cartridges containing GH or placebo, disposal container) and will also receive personalized instruction on how to

prepare and deliver GH using a mock system by study personnel. Patients will be instructed to rotate injection sites to minimize discomfort.

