Randomization and Assignment of Groups. Patients will be assigned to placebo or GH treatment groups using a block randomized assignment schedule that maintains equal group sizes. All included patients will be assigned unique identification numbers by [name], clinical research coordinator in [name] lab, with no involvement in this study design or interpretation of any resultant data. [name] will then assign identification numbers in a consecutive fashion to either group "maize" (randomly designated by [name] as either the placebo or treatment group) or group "blue" (the group not selected to be represented as group A). [name] will keep all patient names and assigned identifier lists private in a sealed envelope in a locked cabinet as well as on two separate passcode protected hard drives. He will make the unblinded group identities available to [name], relevant members of the UMHS Pharmacy IDS and safety board members if necessary. Therefore, the patients, investigators, attending physicians, those measuring outcome will be unaware of the allocation of the patients and thus will be blinded.

Risks of Participation. There are some potential risks of GH that will be closely monitored. The risks include: glucose intolerance or reduced insulin sensitivity, fluid retention and peripheral swelling, joint pain, headache, numbness or fatigue, tissue atrophy, pancreatitis, intracranial hypertension, injection site lipoatrophy, and local or systemic allergic reactions. The injection of GH might infrequently cause some slight discomfort and there is a rare risk of infection from injections. There are minimal risks associated with the blood draws -- the needle stick may infrequently hurt and cause bruising, and a rare risk of local infection. There are no known harmful effects from the strong magnetic field used for MRI, although any loose metal object has the risk of causing damage or injury if it gets pulled toward the strong magnet. Strength measurements might infrequently cause some soreness that would last less than a day.

Benefits of Participation. If our hypothesis is supported, patients that receive GH will have improved recovery after ACL-R.

Payment to Subjects. Patients will also receive \$1000 for participating in the study. Patients who drop out prior to completion will receive a pro-rated amount (\$125 per visit).

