Outcome Measures. The overall objectives of the study are to evaluate if GH is safely tolerated in closely monitored patients undergoing ACL-R, and if so, to collect pilot and early efficacy data to determine if subsequent larger clinical trials are warranted. The primary outcome measure of the study is isokinetic knee extension strength at 26 weeks. Secondary outcome measures include isokinetic strength at other time points, MRI measurement of muscle size, PROMs, and circulating protein biomarkers (IGF-1, myostatin, MMP-3, and hyaluronic acid).

Sample Size and Statistical Analyses. We base the sample size for this study on maximum isokinetic knee extension values at the time of discharge from our previous study (Mendias 2013). To detect a 30% difference in isokinetic knee strength between the placebo and GH group, with a power of

80% and $\alpha=0.05$, requires $N=17$ per group. To account for any patient attrition, we will aim to recruit 7 additional patients for each group into the study for a total of $N=24$ per group or $N=48$ for the entire study. We will use a mixed-effects linear regression model (Zhang 2010) to look at the changes in individual parameters between the placebo and GH groups at multiple time points over the course of the study, as well as the associations between changes of multiple parameters. We will also perform interim data analysis to determine if there are significant differences in strength and other outcomes between groups.

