Data and Safety Monitoring Plan. We will have a committee to oversee the safety and adverse events that may come up in this study. The committee will consist of [name] (endocrinologist), [name] (sports medicine orthopaedic surgeon), and [name] (primary care/sports medicine). All lab reports will be sent to [name] as they occur, and the full committee will review outcomes and patient (surveys, strength measurements, M-Labs blood work reports, injuries, etc.) every 3 months (or as needed) and review. If an excessive number of adverse events or infrequent but serious events happen, the committee will have the ability to halt the study or unenroll patients from the study. The committee may also stop the trial if there are any concerns that GH is causing harm. These potentially serious events that would cause the patient to unenroll from the study include any vital signs rising to levels above those described in the exclusion criteria, or signs of intracranial hypertension, severe fluid retention, severe hyperglycemia. These are potentially serious side effects described from previous clinical trials of GH, and although we cannot predict all potentially serious side effects, we will rely on the clinical expertise of the safety monitoring team to assess any other potentially serious but unexpected risks. In these situations the random code will be broken for that patient and any required care for them will then be initiated. Unblinding for all study team members will occur after the last patient has been discharged from care.

At the conclusion of the study, original data will be archived in the UM Department of Orthopaedic Surgery following FDA guidelines.

Adverse Event Reporting Timetable. We will follow the standard IRB adverse events reporting timeline. Adverse events that are expected and non-serious will be reported to the safety committee at their regular meetings, and to the IRB as part of the scheduled continuation application. Serious adverse events will be reported to the safety committee immediately, and to the IRB within 7 days, and to the FDA as per the regulations.

Regulatory Affairs Coordinator. [name], clinical research manager in the Department of Orthopaedic Surgery, will coordinate safety committee meetings and ensure the study maintains regulatory compliance with federal and state laws, and UM policies.

References

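### The trigger for unblinding the study team is the last discharge, with no requirement that MRI volumes, ELISAs and a database lock come first, so these secondary outcomes may be measured with allocation known

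*Combined protocol and SAP*

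**What the plan says.** Five places in the protocol bear on this point.

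- **Data and Safety Monitoring Plan**, on opening the code: "Unblinding for all study team members will occur after the last patient has been discharged from care". No team member is exempted. The only other end-of-study data step described is archiving.
- **Table 1, Postop 6 (about 26 weeks)**: "Surveys, BioDex (isometric, isokinetic, balance), MRI, blood draw, vital signs, patient discharged from the study".
- **MRI Muscle Volume Measurements**: "Bilateral MRI scans will be performed at the pre-operative, third post-op and sixth post-op visit". On what follows the scan: "The volume of the quadriceps and hamstring muscle groups will be determined using quantitative MRI analysis software". No reader, read date or masking of scans is given.
- **Blood Draw**: part of each sample goes to the clinical laboratory, and "a portion will be stored at -80°C for measurement of different proteins". Those proteins are myostatin, MMP-3 and hyaluronic acid, run by ELISA in duplicate. No assay date is given. IGF-1 is on the clinical laboratory's list.
- **Randomization and Assignment of Groups**: "those measuring outcome will be unaware of the allocation of the patients and thus will be blinded". No duration is attached to this statement.

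On the standing of the affected measures, **Outcome Measures** says: "Secondary outcome measures include isokinetic strength at other time points, MRI measurement of muscle size, PROMs, and circulating protein biomarkers". The primary outcome is isokinetic knee extension strength at 26 weeks.

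**The concern.** The event that allows the code to be opened is the end of patient visits, not the end of outcome measurement. For MRI volume and the three ELISA biomarkers these are different times, because the visit yields a scan and a tube of blood and the outcome value is produced later. If the code is opened in between, the person producing the value may know the patient's group.

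What is at stake is detection bias in secondary outcomes. Muscle size bears directly on the study's atrophy hypothesis, and the stated purpose of the early efficacy data is to help decide whether larger trials are warranted. The document gives no rule for handling a poor scan or discordant ELISA duplicates. Any such decision would be left to whoever does the work, and it should be made without knowledge of the group.

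**Working it through.** The plan gives no figure to reproduce here. The check is the order of events, followed by a count of what could be exposed.

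**Order of events**

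1. The last patient attends Postop 6. Strength, surveys, vital signs, MRI and blood draw are done, and the patient is discharged from the study (Table 1).
2. From this point the condition for unblinding the whole team can be met (Data and Safety Monitoring Plan).
3. Volumes are determined from the scans with software (MRI Muscle Volume Measurements), and ELISAs are run on frozen samples (Blood Draw). Neither step has a date.
4. Query resolution and database lock are not described anywhere, so neither can serve as a condition for step 2.

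Nothing places step 3 before the code is opened. The blinding statement under Randomization and Assignment of Groups follows from how the allocation list is held. Once the list is opened to the whole team, that basis no longer applies.

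**Which outcomes are exposed at measurement**

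| Outcome | When the value is produced | Exposed at measurement? |
|---|---|---|
| Isokinetic strength at 26 weeks (primary) | At the visit, as the highest of five trials | No |
| Patient-reported outcomes | At the visit, by the patient | No |
| IGF-1 | By the clinical laboratory | Less so |
| MRI muscle volume | After the scan, date not stated | Possible |
| Myostatin, MMP-3, hyaluronic acid | After the draw, from frozen samples, date not stated | Possible |

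**How many scans and samples**

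Inputs: up to 48 patients (Patient Selection and Recruitment), MRI at 3 visits (Preop 2, Postop 3, Postop 6), and blood draws at 7 visits (Preop 1 and Postop 1 to 6), all from Table 1.

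- Bilateral scans: 3 × 48 = 144 at most, of which 48 are at 26 weeks.
- Blood draws: 7 × 48 = 336 at most, assuming that a portion of every draw, including the screening draw, is stored.

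| Assumed timing of reads and assays | Scans exposed | Draws exposed |
|---|---|---|
| All finished before the code is opened | 0 | 0 |
| Only the last patient's final scan and sample outstanding | 1 of 144 (0.7%) | 1 of 336 (0.3%) |
| All 26-week scans and samples outstanding | 48 of 144 (33%) | 48 of 336 (14%) |
| Everything batched after unblinding | 144 of 144 | 336 of 336 |

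The document does not say which row applies. Recruitment may stop below 48, which would lower the ceilings in proportion.

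**The case against.** The strongest reply is that the word *after* fixes only an earliest time. A team that finishes every read and assay, and then opens the code, complies with both the unblinding sentence and the blinding statement. This is right, and it limits the point in several ways.

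- **A contradiction between the two sections.** A reader might infer one. The text does not support it, because both statements can be met together. The gap is that nothing obliges the team to meet both.
- **Certain exposure of the last patient's scan and sample.** A reader might infer this from the shared visit. No unblinding date is given, so the documented minimum is zero. The unblinding sentence also speaks of discharge from care, while Table 1 speaks of discharge from the study. If the former comes later, the gap narrows, but there is still no lock.
- **Reading by the trial's own team.** The MRI section does not say who reads the scans or where. The owner of the laboratory running the ELISAs is a removed name. A reader outside the study team is not excluded.
- **Bias in the strength measurement.** The strength section gives a mechanical best-of-five rule, and the value is recorded at the visit, before the trigger.
- **Batching at the end.** The planned interim analysis of strength and other outcomes suggests that some data are processed during the trial. It does not name MRI or ELISA, so it neither establishes nor rules out late batching.

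It can also be said that this is a pilot with coded identifiers, masked group labels and a sealed list. Those safeguards work until the code is opened. They do not govern what must be finished first.

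**Conclusion.** The point holds as an unguarded permission. As written, the plan allows MRI muscle volumes and three ELISA biomarkers to be measured after the team has been unblinded, and it leaves the blinding of outcome measurers unprotected from the last discharge onward. It does not plan or require unblinded measurement.

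The size is not known from the document: from nothing up to 144 bilateral scans and all stored samples. The upper end assumes full recruitment of 48 and processing entirely after unblinding. Any resulting bias further assumes that the measurers are among those unblinded, and that reading scans or handling assay results involves some judgement. The document is silent on both.

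Exposure at measurement is confined to these secondary outcomes. This is a worthwhile and inexpensive improvement, not a flaw that undermines the primary result.

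**What to change.** Replace the unblinding sentence in the Data and Safety Monitoring Plan with one to this effect: study team members are unblinded only after (i) the last 26-week visit, (ii) completion of all MRI volume measurements and all ELISAs on coded data, (iii) resolution of data queries, and (iv) database lock. State that emergency code breaks for a single patient are separate and unchanged. A matching clause under Randomization and Assignment of Groups should say that those measuring outcomes remain blinded until that lock.

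The change needs no extra visits or patient procedures. Its cost is a short delay in unblinding while the last reads and assays are finished, queries are resolved and the database is locked.
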